#### **Postoperative Procedures:**

*SOC (mandated for study purposes):* Following completion of the procedure in the operating room, an infusion pump (Infutronix, Natick, Massachusetts) with a 500 mL ropivacaine 0.2% reservoir will be attached to the perineural catheter. For patients in the **continuous infusion** group, the pump will provide an 8 (infraclavicular) or 6 (sciatic) mL/h basal infusion and a 4 mL patient-controlled bolus with a 30-minute lockout (standard at UCSD).

*Experimental:* For patients in the **titratable automated intermittent bolus** group, the pump will provide an automatic 11 (infraclavicular) or 8 (sciatic) mL bolus once every 2 hours and have a 4 mL patient-controlled bolus with a 30 minute lockout. In addition, for those in the **titratable automated intermittent bolus** group, the infusion pump will be set in a “pause” mode that delays initiation of the automated bolus doses by 5 hours (this can be over-ridden by patients if they would like to initiate their perineural infusion earlier than 5 hours). Lastly, subjects in the **titratable automated intermittent bolus** group will be able to titrate the volume of their automated bolus up or down within the range of 1-16 mL.

*Per standard of care,* the pump will not administer more than 20 mL during each hour (below the current UCSD maximum). Prior to discharge, the functioning of the infusion pump will be explained, so that they understand that they should push the bolus button if they have pain. This is accurate regardless of which treatment group the patient is randomized to, ensuring that all subjects will receive adequate analgesia.

*Experimental:* Subjects will be contacted via phone for the 9 days following surgery to collect information regarding surgical pain (Numeric Rating Scale of 0 to 10, with “0” being no pain and “10” being the worst pain ever experienced), analgesic use, sleep disturbances, infusion side effects, and satisfaction with pain control. When 500 mL has been infused or on Day 8—whichever comes first—subjects will remove the catheter and

place the pump in a pre-addressed and -stamped package for return [note that it is standard of care for patients to remove the catheters at home; but, listed as experimental here due to the timing of catheter removal which will be later than is standard of care due to the experimental local anesthetic administration protocol].

**Data Acquisition [all experimental]:**

Data will be gathered from the patients' electronic medical record, by telephone follow-up, and from the memory of each infusion pump. Subjects will be contacted by phone for the 9 days following surgery. Data will be recorded on paper Case Report Forms, including: patient name, medical record number, age, sex, height, weight, surgical procedure, date of procedure, anesthesiology attending overseeing/placing catheter, randomization number, whether a femoral/saphenous block was placed, if the catheter was placed per protocol, if the block set up successfully, intraoperative fentanyl, morphine and dilaudid, and the time of infusion initiation.

**Outcomes (End Points):** For the first 9 postoperative days, subjects will be asked to answer the questions with regard to the previous 24 hours: opioid consumption, worst pain, average pain, least pain, current pain (Numeric Rating Scale for all pain scores), any numbness on extremity (scale 0=absent to 10=insensate), fluid leakage (yes/no), number of sleep disturbances due to pain (awakenings), satisfaction with analgesia (0=very dissatisfied, 10=very satisfied), the bolus volume for subjects in the titration group, and the seven questions of the Brief Pain Inventory's Interference Scale. The date and time of infusion completion will be recorded as will the reason for catheter removal (reservoir exhaustion vs. another reason).

**Statistics:** The infraclavicular and popliteal-sciatic groups will be analyzed separately as two distinct analyses. This study will be powered for two primary end points: (1) the average NRS queried on postoperative day 1; and (2) the duration of treatment from when the infusion pump was initially turned on until the local anesthetic reservoir was exhausted [recorded by the infusion pump memory]. The dual hypotheses will be tested with a serial testing strategy, such that Hypothesis 2 will not be formally tested unless the conclusion of Hypothesis 1 is at least "noninferiority". Following the approach described in Althunian et al, noninferiority will be assessed by comparing the lower limit of the 95% confidence interval for the difference (CB minus AB) on the NRS (range: 0 to 10) to a pre-specified noninferiority margin of 1.7 NRS units (see Figure 1). This will provide evidence that the analgesia provided by the novel automated boluses is no worse than 1.7 NRS units compared to CB.

*Noninferiority margin and framework for concluding noninferiority or not. Adapted from Althunian et al.*

[figure not shown]
Baseline characteristics of the randomized groups will be summarized with means, standard deviations, and quartiles. Balance between groups will be assessed following the approach described by Schober, et al.

Specifically, standardized differences will be calculated using Cohen's d whereby the difference in means or proportions is divided by the pooled standard deviation estimates. Any key variables (age, sex, height, weight, and BMI) with an absolute standardized difference  $>0.47$  (based on Austin, 2009 with  $1.96 \times \sqrt{2/n} = 0.47$ ) will be noted and included in a linear regression model to obtain an estimate of the treatment group differences adjusted for the imbalanced covariate(s). If residuals from the linear regression indicate violations of key assumptions (i.e. homoscedasticity or Gaussian distribution), data transformations and/or alternative generalized linear models will be applied as appropriate.

Secondary outcomes will also be analyzed by Wilcoxon-Mann-Whitney test, or linear models (or generalized linear models) as appropriate with covariates for any imbalanced covariates. No multiplicity adjustments will be applied for these analyses. End points will be analyzed for each day (e.g., opioid consumption on Day 2) as well as all days combined (e.g., cumulative opioid consumption Days 1-9).

**Sample size estimate:** Power is simulated based on the distribution of pain measured with the Numeric Rating Scale (NRS) observed in the "Above bifurcation" group in Monahan, et al. (*Anesth Analg* 2016;122:1689-95) for the sciatic catheter group. For the infraclavicular group, we simulated NRS scores from the basal/bolus treatment from [name] et al. (*Anesthesiology* 2004;100:395-402). Specifically, we simulate NRS scores from a discrete distribution as depicted in Figure 1, panel A (infraclavicular) and Figure 2 (sciatic). This results in an expected interquartile range of approximately 1 to 4, and a median of approximately 3 NRS units. We simulated 1000 trials in which the two groups, n=35 per group, were assumed to follow the same discrete distribution, submitted each trial to a Wilcoxon-Mann-Whitney test, and derived 95% confidence intervals (Bauer 1972; Hothorn, et al. 2008). Out of the 1000 trials, 792 (79.2%) correctly resulted in a conclusion of non-inferiority; suggesting that the probability that the trial correctly concludes non-inferiority is about 80% when the groups follow exactly equivalent distributions.

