## 7. BACKGROUND AND SIGNIFICANCE

**Continuous peripheral nerve blocks:** In the postoperative setting, pain is a primary concern of patients and healthcare providers. Over 40% of ambulatory patients undergoing orthopedic procedures experience moderate-to-severe postoperative pain at home. A single-injection peripheral nerve block provides up to 15 and 24 hours of analgesia following upper and lower extremity procedures, respectively. However, following this initial period, patients must rely on other, less potent, analgesics such as oral and intravenous opioids. A continuous peripheral nerve block (CPNB)—also called perineural local anesthetic infusion—offers an alternative analgesic option. This technique involves the percutaneous insertion of a catheter directly adjacent to the peripheral nerve(s) that innervate the surgical site at the same time the initial regional block is placed. During the past decade, ultrasound-guided catheter placement has also become the common method for placing perineural catheters. Using this technique, the peripheral nerve(s) is visualized in real-time using ultrasound, and then the catheter is placed directly adjacent to the nerve(s), also under real-time ultrasound guidance.

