### Preoperative Procedures:

*SOC (mandated for study purposes):* Following written, informed consent, subjects will have baseline anthropometric information (e.g., age, sex, height, weight) collected and a sciatic perineural catheter inserted by a regional anesthesia fellow or resident under the direct supervision and guidance of a regional anesthesia attending (or by the attending him/herself).

*Per standard of care,* all subjects will have an ultrasound-guided infraclavicular or popliteal-sciatic perineural catheter inserted as previously described.

*SOC (mandated for study purposes):* After catheter insertion, ropivacaine 0.5% (20 mL, with epinephrine) will be administered via the catheter under ultrasound visualization. Sensation in the brachial plexus or tibial/peroneal nerve distributions will be checked for anesthetic effect. A “successful” regional block will be defined as sensory- and motor-block onset within the 30 minutes following the local anesthetic injection.

A saphenous nerve block with ropivacaine 0.5% (and epinephrine) may or may not be provided, depending on the surgical procedure, *per standard of care*.

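### Sciatic analysis: the recorded, optional saphenous block is not adjusted for in the POD 1 pain comparison, which may cost some precision but does not bias the result

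*Combined protocol and SAP*

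**What the plan says.** **The block.** Section 9, Preoperative Procedures: "A saphenous nerve block with ropivacaine 0.5% (and epinephrine) may or may not be provided, depending on the surgical procedure". No rate of use is given. The block can arise only in the popliteal-sciatic cohort, which is analyzed separately from the infraclavicular cohort.

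**Recording.** The case report form items in Section 9, Data Acquisition, include "whether a femoral/saphenous block was placed" and the surgical procedure.

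**Timing.** Section 7: "A single-injection peripheral nerve block provides up to 15 and 24 hours of analgesia following upper and lower extremity procedures, respectively". This is a general statement and is not specific to the saphenous nerve. The first primary end point is average NRS on POD 1, and in the daily calls "subjects will be asked to answer the questions with regard to the previous 24 hours".

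**Adjustment.** The Statistics text checks balance on "Any key variables (age, sex, height, weight, and BMI) with an absolute standardized difference" above 0.47 and moves any flagged variable into a linear regression. Neither the saphenous block nor the surgical procedure is on the list, and the Randomization paragraph names no stratification factor. The sample size text bases noninferiority on a Wilcoxon-Mann-Whitney interval. The plan does not say which result decides noninferiority if the regression is also fitted.

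**The concern.** The five listed variables are age, sex and three measures of body size. None describes analgesia or surgery. The saphenous block is a second analgesic given to some patients and not others. It acts outside the territory of the study catheter, plausibly during much of the POD 1 recall window, and it marks the type of operation. It is therefore a more natural candidate for adjustment than height or weight, and it is already collected.

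What is at stake is efficiency at the first step of the serial test. Stated noninferiority power is 79.2%, and treatment duration is formally tested only if noninferiority is concluded. A prognostic factor left in the residual variance lowers the chance of passing that step.

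**Working it through.** **Inputs from the plan:** n=35 per arm, margin 1.7 NRS, limit of a two-sided 95% interval (one-sided 0.025), trigger 0.47. **Assumptions, because the plan gives no figure:** block use p=50% (30% to 70% as a range), block effect on POD 1 NRS of 0 to 2 points, total SD 2.5.

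**1. The plan's trigger.** 1.96 × √(2/35) = 0.4685, which matches 0.47.

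**2. The SD.** The 79.2% cannot be reproduced exactly, because the simulated distribution is in a figure that is not available. By the normal formula it corresponds to SD = 1.7 / [(1.960 + 0.813) × √(2/35)] = 1.7 / 0.663 = 2.56. The stated interquartile range of 1 to 4 suggests 3/1.349 = 2.22, with power of 89%. An SD of 2.5 gives about 0.80 in the simulation below, close to the stated power.

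**3. Chance imbalance.** The SD of the between-arm difference in block use is √(2p(1−p)/35): 0.120 at p=0.5 and 0.110 at p=0.3 or 0.7. The 95% range is about ±22 to 23 percentage points. By exact binomial calculation, a gap of at least 20 points (7 of 35 patients) arises in 12.0% of trials at p=0.5 and 8.9% at p=0.3 or 0.7.

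**4. Would the trigger catch it?** At p=0.5, 0.4685 corresponds to a gap of 0.4685 × 0.5 = 0.234. A 20-point gap has a standardized difference of 0.20/0.5 = 0.40 and passes unadjusted. The trigger fires in 5.7% to 6.1% of trials across p=0.3 to 0.7.

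**5. Variance attributable to the block.** e²p(1−p)/SD² = 0.25e²/6.25, which is 1%, 4%, 9% and 16% for e = 0.5, 1, 1.5 and 2.

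**6. Operating characteristics.** Simulated trials with normal-theory intervals, block independent of allocation (60,000 per setting; 100,000 for the zero-effect row):

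| Assumed effect (NRS) | Type I error at the margin, unadjusted | Power, unadjusted | Power, block added to the 0.47 list | Power, always adjusted |
|---|---|---|---|---|
| 0 | 0.025 | 0.800 | not run | 0.794 |
| 0.5 | 0.0246 | 0.800 | 0.799 | 0.798 |
| 1 | 0.0253 | 0.801 | 0.802 | 0.811 |
| 1.5 | 0.0255 | 0.800 | 0.803 | 0.830 |
| 2 | 0.0257 | 0.798 | 0.805 | 0.858 |

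The unadjusted estimate has bias of about 0 throughout. Type I error under constant adjustment is also about 0.025. For effects of 0.5 to 2, adjusted and unadjusted conclusions differ in about 3%, 5%, 7% and 10% of trials when the arms are truly equal, and in about 1% to 2% at the margin. Differences of 0.002 to 0.003 in power are within simulation error.

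**The case against.** **Chance imbalance is already in the interval.** A reader might infer that imbalance in block use undermines the noninferiority conclusion. A 20-point gap with an effect of 1 to 2 NRS moves the estimate by 0.20 × 1 = 0.2 to 0.20 × 2 = 0.4, or 12% to 24% of the 1.7 margin. That describes one unlucky draw. Over repeated trials the unadjusted 95% interval carries this variation, and its error rate stays at 0.025. This objection stands, and it limits the point to precision.

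**The bias route is only conditional.** A reader might also infer that the block could be chosen with the allocation known. The block is described under Preoperative Procedures, ahead of Randomization, and is tied to the operation, not the arm. The Table of Events lists a single-injection block before randomization, although that row may mean the catheter bolus. No sentence fixes the order of the saphenous decision and the envelope, so this is a gap to close and not evidence of bias.

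**The effect may be small.** The duration quoted from Section 7 is an upper limit, and a preoperative block spends part of it in surgery. The block lowers pain while the surgery it marks may add pain, so the net effect could be near zero. At 0.5 NRS, adjustment gains nothing. This stands as a limit on size.

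**Duration.** Patients who press the bolus button for pain outside the sciatic territory would empty the reservoir sooner. The documents give no figure for this and nothing to suggest that it differs between arms, so no effect on the duration result is claimed.

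**Why this variable?** The same argument applies to other prognostic factors, including surgical procedure, which is also recorded. That is fair. A yes/no block indicator is simply practical with 35 per arm.

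**Conclusion.** The point holds as a matter of efficiency, in the popliteal-sciatic analysis only. A recorded and plausibly prognostic co-analgesic is left out of the adjustment set, and adding it to the existing list would change almost nothing because the 0.47 rule would act on it in about 6% of trials. Adjusting for it in every trial changes noninferiority power by about −0.5 percentage points (no effect), 0 (0.5 NRS), +1 (1 NRS), +3 (1.5 NRS) or +6 (2 NRS).

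These figures rest on assumed 50% use, total SD 2.5 and normal-theory intervals. The plan's Wilcoxon interval will give somewhat different values. Neither the rate of use nor the effect of the block is in the documents. Bias and inflated type I error are not shown, and would need the block decision to depend on allocation.

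**What to change.** 1. In the Statistics text, prespecify that the sciatic POD 1 NRS comparison is adjusted for saphenous block (yes/no) whatever the observed balance, for example by a stratified (van Elteren) Wilcoxon test with a matching stratified interval for the shift. Treat the duration comparison in the same way for consistency.
2. State that this stratified interval is the one compared with the 1.7 margin, so that it cannot compete with an unadjusted interval or a regression estimate.
3. Record the planned use of the block before the envelope is opened, and adjust for that recorded plan. The covariate is then a true baseline variable and the question of order is settled. Care is unchanged, and any departure from the plan is simply recorded.

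**Cost:** a few sentences in the plan, one extra entry on the case report form (actual use is already there), a slightly more complex interval calculation, and about half a percentage point of power if the block turns out not to be prognostic. No extra patients are needed.

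### Does it matter that the plan does not say which analysis decides Hypothesis 1 when baseline imbalance triggers a regression, transformation or GLM?

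*Combined protocol and SAP*

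**What the plan says.** All the relevant text is in section 9 of the combined protocol and SAP.

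- **Decision rule (Statistics).** Hypothesis 1 compares the lower 95% limit of the day-1 pain difference, continuous minus automated bolus, with a "pre-specified noninferiority margin of 1.7 NRS units". The text places that difference on the 0 to 10 NRS. It does not name the estimator.
- **Gate (Statistics).** "Hypothesis 2 will not be formally tested unless the conclusion of Hypothesis 1 is at least" noninferiority. The two catheter cohorts are analysed separately, so each has its own gate.
- **Imbalance step (paragraph on baseline characteristics).** Any of five key variables with an absolute standardized difference above 0.47 "will be noted and included in a linear regression model to obtain an estimate of the treatment group differences", adjusted for that variable. If the residuals violate the model assumptions, "data transformations and/or alternative generalized linear models will be applied as appropriate". No outcome, hypothesis or margin is mentioned here.
- **Secondary outcomes.** "Secondary outcomes will also be analyzed by Wilcoxon-Mann-Whitney test, or linear models (or generalized linear models) as appropriate".
- **Sample size estimate.** For Hypothesis 1 the simulation "submitted each trial to a Wilcoxon-Mann-Whitney test, and derived 95% confidence intervals", with no covariates. If noninferiority is concluded, duration is then tested by Wilcoxon-Mann-Whitney, introduced with the word *again*.

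**The concern.** The imbalance step comes directly after the noninferiority framework, and the word *also* in the secondary-outcome sentence suggests that it covers the primary end points. On that reading, two or more analyses could each claim to decide Hypothesis 1: the Wilcoxon interval, an adjusted mean difference, and a model on some other scale chosen after looking at residuals. No order of precedence is written down.

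The last of these looks the most troublesome. The margin is an additive 1.7 units and has no single equivalent on a ratio or log scale. If an analyst could choose the scale and the conversion after seeing the data, the conclusion on Hypothesis 1, and with it whether Hypothesis 2 is tested at all, might depend on that choice. Chance imbalance would decide when the choice arises. A flexible gate matters in a serial testing scheme because the second test borrows its protection from the first.

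**Working it through.** **1. The plan's own threshold.** With n = 35 per arm, 1.96 × √(2/35) = 0.4685, which rounds to the stated 0.47. Each variable therefore crosses the line by chance in about 5% of cohorts.

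**2. How often the regression is triggered.**
- Five independent variables: 1 − 0.95⁵ = 22.6%.
- Allowing for the dependence among sex, height, weight and BMI (20,000 simulated cohorts, assumed covariate distributions): 19.25%.
- At least one of the two cohorts: 1 − (1 − 0.1925)² = 34.8%.

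**3. The stated power.** The plan reports 79.2% (792 of 1000) with an "expected interquartile range of approximately 1 to 4, and a median of approximately 3 NRS units". The simulated distribution is in a figure that is not available, so an exact reproduction is not possible. Three assumed whole-number distributions with quartiles 1, 3 and 4 give rank-interval power of 67.8%, 76.4% and 79.0%. The stated figure is consistent with a Wilcoxon interval.

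**4. Wilcoxon against untransformed regression, in triggered cohorts.** The assumed pain distribution has mean 3.24 and SD 2.34. One covariate, unrelated to pain, is imbalanced beyond 0.47. There are 6,000 triggered trials per row. The rank limit is the 446th ordered pairwise difference. A trial passes if the lower limit exceeds −1.7.

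| True difference | Wilcoxon passes | Regression passes | Either passes | Disagree |
|---|---|---|---|---|
| 0 | 74.3% | 81.1% | 82.9% | 10.3% |
| 1.7 units worse | 0.8% | 2.45% | 2.5% | 1.7% |

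With no true difference, disagreement over all cohorts is 0.1925 × 0.103 = 2.0%. Across five assumed distributions, with age explaining 0 or 10% of latent pain, disagreement was 4–13% of triggered cohorts, or 0.7–2.6% of all cohorts.

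The second row is the one that bears on validity. A two-sided 95% interval allows 2.5% false noninferiority, and even the most permissive reading (either may pass) reaches 2.5% and no more. Mixing in the cohorts where only Wilcoxon applies, and taking its error there as 0.8% too, the overall rate is 0.8075 × 0.8% + 0.1925 × 2.5% = 0.65% + 0.48% = 1.1%.

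**5. The margin on other scales.** As a ratio, (m + 1.7)/m is 2.70, 1.57 and 1.425 at m = 1, 3 and 4. On log(NRS + 1), ln((m + 2.7)/(m + 1)) is 0.615, 0.354 and 0.293. So there is indeed no single converted margin. But the decision rule asks for a difference on the NRS in NRS units. A transformed or log-link result does not meet that rule until it is converted back to an NRS difference, so the margin has no need to move.

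**6. Reading the passages together.** The imbalance step asks for an adjusted *estimate*. The sentence that opens the gate refers to *the test* for Hypothesis 1, then applies Wilcoxon *again*. The word *also* in the secondary-outcome sentence precedes Wilcoxon first, so it supports Wilcoxon as the primary test at least as strongly as it supports models. The natural reading is that Wilcoxon decides, with an adjusted estimate reported alongside when a baseline variable is out of balance.

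**The case for a change.** The best case for a change is that nothing in the text labels the regression or its successors as supportive, and the transformation branch could matter. Pain scores bounded at 0 with quartiles near 1, 3 and 4 are skewed, so residual checks may fail often. If log(NRS + 1) were then used with 1.7 converted at a score of 1, false noninferiority would be 12–34% in simulation. One sentence would close the matter at almost no cost.

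The first part stands: the label is missing. The rest is weaker. How often residuals fail depends on a check the plan does not name. Shapiro-Wilk or Breusch-Pagan at 5% fails in 47–87% of triggered cohorts. A rule of absolute skewness above 1 fails in 1–15%, which at a 19–20% trigger rate is about 0.2–3% of all cohorts. The 12–34% also needs a conversion point at the lower quartile. Converted at the plan's median of 3, the same analysis gives at most 0.5%. Neither conversion is in the plan, and the rule's own scale argues against both. A clarifying sentence would do no harm, but it would only record what the text already implies.

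**Conclusion.** No change follows. The plan omits a statement of precedence, but the scale and margin for Hypothesis 1 are fixed, the deciding test is strongly implied, and both raw-scale readings are sound. Choosing between them alters the conclusion in roughly 1–3% of cohorts and does not push false noninferiority above 2.5%. Wilcoxon, the implied choice, is the more conservative of the two. The data collected, the sample size, the power simulation and the Hypothesis 2 test are unaffected.

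These sizes rest on assumed pain distributions that match the plan's quartiles, assumed covariate distributions, whole-number scores and 35 per arm. The conclusion depends less on them than on the wording of the decision rule, which keeps the comparison in NRS units. It would be different if the plan had said that a transformed-scale result decides Hypothesis 1. It does not.

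### Does a Wilcoxon interval on whole-number pain scores make the 1.7-point noninferiority margin meaningless?

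*Combined protocol and SAP*

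**What the plan says.** The Statistics paragraph of section 9 decides Hypothesis 1 by "comparing the lower limit of the 95% confidence interval for the difference (CB minus AB) on the NRS" to a "pre-specified noninferiority margin of 1.7 NRS units". It reads success as showing that "the analgesia provided by the novel automated boluses is no worse than 1.7 NRS units compared to CB". It does not name the interval method, and it does not say whether the difference is one of means, medians or a shift.

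The method can be inferred from the sample size text. There, "we simulate NRS scores from a discrete distribution", with an "expected interquartile range of approximately 1 to 4, and a median of approximately 3 NRS units". The sponsor then "submitted each trial to a Wilcoxon-Mann-Whitney test, and derived 95% confidence intervals", citing the rank-based confidence set literature. With 35 per group and identical distributions, 792 of 1000 simulated trials concluded noninferiority. The text that follows says duration will be tested by Wilcoxon-Mann-Whitney again, which confirms the Wilcoxon interval as the intended method for pain.

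Pain is collected on a "Numeric Rating Scale of 0 to 10"; the recording step is not stated. The order of testing is fixed: "Hypothesis 2 will not be formally tested unless the conclusion of Hypothesis 1 is at least" noninferiority.

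**The concern.** The limits of a Wilcoxon interval are ordered pairwise differences between patients in the two groups. If all scores are whole numbers, so are those differences, and the interval cannot distinguish 1.7 from 1.2 or 1.9. A reader could fairly say that the prespecified margin is not the one being applied.

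Two consequences would matter. First, power could be lost needlessly, and because pain is the gate to the duration test, a failure there closes both hypotheses in that cohort. Second, if the claim is read as a mean difference, the error rate at a true difference of 1.7 depends on how the extra pain is spread across patients. A mean-difference interval set against -1.7 would seem to answer both at no cost in patients.

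**Working it through.** **Inputs.** From section 9: 35 per group, margin 1.7, two-sided 95% interval, quartiles about 1 and 4, median about 3, stated power 79.2%. Assumed: whole-number scores, and the score distributions themselves, because the figures with the sponsor's distributions are not shown.

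**Step 1: the whole-number effect.** There are 35 × 35 = 1225 pairwise differences. The lower limit is about the k-th smallest, with k = 1225/2 - 1.96 × √(1225 × 71/12) = 612.5 - 166.9 ≈ 445. With whole-number scores the 445th difference is a whole number. It exceeds -1.7 exactly when it is -1 or more, and the same holds for any margin strictly between 1 and 2. In simulation, margins of 1.01, 1.5, 1.7 and 1.99 gave the same decision in every trial. The margin still selects the band: for a rounded normal (mean 2.7, SD 2.4) power is 0.467 at margin 1.0, 0.790 anywhere between 1 and 2, and 0.957 at 2.0.

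**Step 2: the plan's own figure.** Whole-number distributions with the stated quartiles give Wilcoxon power from 0.67 to 0.91, median 0.81. The rounded normal above gives 0.790 and a beta-binomial with mean 3 gives 0.801. The stated 0.792 sits in the middle of this range. It cannot be reproduced exactly without the figure, but it is what a Wilcoxon interval on whole numbers delivers.

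**Step 3: Wilcoxon against Welch, identical groups.** Probabilities for scores 0 to 10:

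- A: .17, .12, .14, .19, .15, .09, .06, .04, .02, .01, .01 (SD 2.28)
- B: .20, .10, .13, .18, .15, .07, .06, .05, .03, .02, .01 (SD 2.46)
- C: .14, .13, .16, .20, .16, .09, .06, .03, .02, .01, 0 (SD 2.08)
- X: .13, .13, .16, .22, .16, .03, .02, .03, .05, .04, .03 (SD 2.62)

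All four have quartiles 1, 3 and 4.

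| Distribution | Wilcoxon, any margin in (1, 2) | Welch, margin 1.7 |
|---|---|---|
| A | 77.4% | 86.6% |
| B | 71.1% | 81.4% |
| C | 83.2% | 91.9% |
| X | 80% | 76% |

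The quartiles do not fix the SD, and Welch power depends on it, roughly as Φ(1.7/(SD × √(2/35)) - 1.96): 0.945 at SD 2.0, 0.842 at 2.4, 0.781 at 2.6. X fits the stated quartiles and nearly matches the 79.2%, yet it favours Wilcoxon.

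Random distributions do not settle the matter. Welch was ahead in 97.5% of 360 drawn around A, but in only 48% of 300 drawn without a preferred shape (median difference about -0.4 points, worst -29).

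**Step 4: error at a true worsening of 1.7.** If every patient is 1 or 2 points worse, false noninferiority is 0.8-0.9% for Wilcoxon and about 2.5% for Welch. Wilcoxon then behaves like a margin near 1.5, where its error is 2.4-2.5%. Wilcoxon exceeds 2.5% (4.4-7.3%) in the pattern where about a quarter of bolus patients score 10 and the rest are unchanged.

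That case is an error only if the target is the mean. Take A, with mean 3.01. The fraction moved to 10 is q = 1.7/(10 - 3.01) = 0.243. For two independent draws from A, the chance of a tie is Σp² = 0.1354, and the chance of a difference of exactly -1 is 0.1147. Hence P(≤ -1) = (1 - 0.1354)/2 = 0.4323 and P(≤ -2) = 0.4323 - 0.1147 = 0.3176. With the shifted group:

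- P(difference ≤ -2) = 0.757 × 0.3176 + 0.243 × 0.98 = 0.479
- P(difference ≤ -1) = 0.757 × 0.4323 + 0.243 × 0.99 = 0.568

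The median pairwise difference, which is what the Wilcoxon interval targets, is therefore -1, inside the margin. B and C also give -1.

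**Step 5: recording step.** With half-point scores the band narrows to margins between 1.5 and 2, and for the rounded normal the powers are 0.90 (Wilcoxon) and 0.91 (Welch).

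**The case for a change.** The strongest case for a change is that a prespecified margin should act as written, and here 1.7 acts as a band. For score distributions that taper smoothly at the top, which is a natural shape for postoperative pain, a Welch interval at 1.7 usually has more power. When probabilities were not allowed to rise from score 5 to 10, it was ahead in 97.5% of 120 random distributions, by a median of 7 points. Naming the interval would cost one sentence, and the sponsor holds the distributions needed to rerun the simulation. The section's regression adjustment for imbalanced covariates adds some ambiguity about which estimate decides.

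The arithmetic stands, and so does the likely gain for tapering tails. The need for a change does not. The plan's sample size was justified with the same kind of interval, so the planned power of about 80% is not undermined. The switch also has a price: the target becomes a mean difference, the gain can reverse with a heavy upper tail, and acceptance of a true 1.5-point worsening rises from 2.4-2.5% to 5.1-5.7%. The regression ambiguity is small: an assumed trigger rate of 18.5-19.7% times disagreement of 7.8-14.7% when triggered gives 1.4-2.9% of trials. Stating in the plan that the lower limit must be -1 or higher would alter no result, because the Wilcoxon interval already imposes it.

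**Conclusion.** The plan can stand. On whole-number scores the implied Wilcoxon interval concludes noninferiority when its lower limit is -1 or higher. That is at least as strict as 1.7 on the interval's own scale and conservative under a uniform shift. An analyst following the sample size text would apply it without difficulty. The 79.2% power appears to include the coarseness and is not shown to be wrong.

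A mean-difference interval is a legitimate alternative, worth roughly +9 to +10 points of power under A, B and C (for example 86.6 - 77.4 = 9.2) and about -4 under X (76 - 80). Which applies depends on distributions the documents do not show, so this is a trade-off between two defensible targets.

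The conclusion rests on whole-number recording, on the Wilcoxon interval being the decision rule (inferred from the sample size text), and on reading the difference as a shift or median pairwise difference. The Statistics paragraph never specifies a mean. If half-points are recorded, the concern largely disappears.
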